7. STUDY PARTICIPANTS

7.1 Overall Description of Study Participants

Male and female patients aged >18 years old who have been diagnosed with chronic limb threatening ischaemia or severe intermittent claudication that are referred to secondary care to undergo lower limb revascularisation using intravascular lithotripsy.

Clinicians performing the intravascular lithotripsy procedure on study participants

7.2 Inclusion Criteria

Patient participants:

- 1. Adults (>18 years of age)
- 2. Diagnosed with symptomatic PAD (severe incapacitating intermittent claudication or chronic limb threatening ischaemia -Rutherford stages 4–6)
- 3. Referred to secondary care to undergo lower limb revascularisation using intravascular lithotripsy
- 4. Able to understand written and spoken English
- 5. Is willing and able to give written informed consent for participation in the study

Healthcare professionals:

The clinicians who have performed the intravascular lithotripsy procedure on participants included in this research study.

7.3 Exclusion Criteria

Patient participants:

The participant may not enter the study if ANY of the following apply:

- 1. Female participants who are pregnant, lactating or planning pregnancy during the course of the study.
- 2. Patients who do not have capacity to consent for themselves.
- 3. Patients with life limiting condition whereby conservative management is most appropriate.
- 4. Patients with asymptomatic PAD.
- 5. Patients with acute lower limb threatening lower limb ischaemia.
- 6. Patients not being referred for lower limb revascularisation using intravascular lithotripsy.

8. STUDY PROCEDURES

8.1 Screening and recruitment

Participants attending vascular clinics or vascular wards at the participating NHS sites who have been referred for an intravascular lithotripsy procedure will be identified and approached by GCP trained study investigators and collaborators who will be their usual clinicians. Investigators will be listed on the Delegation of Authority and Signature Log. The clinician responsible for the patients care will provide a brief explanation of the study and supply the patient with a patient information sheet. The participant will be allowed at least 24 hours to consider the information, and will be given the opportunity to question the Investigator, their GP or other independent parties to decide whether they will participate in the study. To allow sufficient time for potential participants to review the PIS and study information, we will contact the potential participants at least 24 hours before the intravascular lithotripsy.

8.2 Consent

Patients

Written and verbal versions of the participant information and informed consent will be presented to the participants detailing no less than: the exact nature of the study; the implications and constraints of the protocol; the known side effects and any risks involved in taking part. It will be clearly stated that the participant is free to withdraw from the study at any time for any reason without prejudice to future care, and with no obligation to give the reason for withdrawal.

If the participant agrees to take part in the study, written informed consent will be obtained by a participant signed and dated version of the latest approved consent form before any study specific procedures are performed. We expect participants to provide written informed consent on the day they are being consented for the intravascular lithotripsy. The person who obtained the consent will be suitably qualified and experienced, and will have been authorised to do so by the Chief/Principal Investigator as detailed on the Delegation of Authority and Signature log for the study. The original signed form will be retained at the study site within the Trial Master File (TMF) or Investigator Site File (ISF) as per standard NHS principles (at each of the NHS sites taking part in this study). A copy of the signed Informed Consent Form will be given to participants and a copy retained in the participant medical notes. A fourth copy will be sent to the patients GP to inform them of their participation in the study.

Healthcare professionals

The clinicians performing the intravascular lithotripsy will be given a participant information sheet and they will be asked to sign a written informed consent form. The person who obtained the consent will be suitably qualified and experienced, and will have been authorised to do so by the Chief/Principal Investigator as detailed on the Delegation of Authority and Signature log for the study. The original signed form will be retained at the study site within the Trial Master File (TMF) or Investigator Site File (ISF) as per standard NHS principles (at each of the NHS sites taking part in this study). A copy of the signed Informed Consent Form will be given to participants.

8.3 Data collection

8.3.1 Main study

This study wishes to obtain the following routinely collected data from the patients' medical records and conduct further analyses* on routinely performed scans at various time points during patients' routine PAD care.

Baseline (pre intravascular lithotripsy) data collection:

- 1. Demographic information (age at time of recruitment, sex).
- 2. Weight/height, resting BP (anthropometric measurements).
- 3. Rutherford stage relating to PAD presentation.
- 4. Ankle brachial pressure index.
- 5. Baseline full blood count results and routine biochemistry, including total cholesterol levels, and lipid profile.
- 6. Baseline serum creatinine and estimated glomerular filtration rate.
- 7. Chronic kidney disease status.
- 8. Diabetes status, duration of diabetes history, and current diabetes medication(s).
- 9. History of previous major cardiovascular events.
- 10. Results of cross-sectional imaging relating to the arterial vasculature e.g. duplex or computed tomographic angiography*
- 11. Smoking status.
- 12. WiFi score.
- 13. Previous operations, including a full surgical and vascular history.
- 14. All concomitant medications as reported by patients.
- 15. Anonymised minutes from multi-disciplinary team meetings relating to the patients care.

Day of procedure (Post intravascular lithotripsy) data collection:

The data collected here will relate to information obtained during the intravascular lithotripsy

- 1. Exact location of the lesion treated,
- 2. Number and size(s) of intravascular lithotripsy catheters used
- 3. Duration of intravascular lithotripsy application per arterial site in seconds
- 4. Exact anatomy (number of occlusions or stenoses) of the arterial lesions present on intraoperative angiography
- 5. Nature of the additional surgical or endovascular treatments taking place
- 6. Duration of the whole procedure
- 7. Immediate complications during the procedure and steps taken to address them (e.g. thrombectomy)
- 8. Patency of the treated lesions
- 9. Level of operators performing the procedures
- 10. Volume of contrast used during the procedure.

Day of discharge data collection:

Where available, the data collected here will relate to the period between the completion of the intravascular lithotripsy procedure and the day of discharge

- 1. Re- interventions of any nature
- 2. Amputations of any nature
- 3. Ankle brachial pressure index.
- 4. Full blood count results and routine biochemistry.
- 5. Major cardiovascular events during inpatient stay.
- 6. Duration of inpatient stay (ward and intensive care where applicable).
- 7. Reason(s) for admission to intensive care if relevant.
- 8. Results of cross-sectional imaging relating to the arterial vasculature e.g. duplex or computed tomographic angiography (all of these are routine care).
- 9. WiFi score.
- 10. All concomitant medications.

30 day post discharge data collection:

The data collected here will relate to the time period between the procedure 30 days post discharge.

- 1. Re-intervention(s) nature and reasons why this occurred.
- 2. Amputation(s) nature and reasons why this occurred.
- 3. Ankle brachial pressure index.
- 4. Major cardiovascular events.
- 5. Results of cross-sectional imaging relating to the arterial vasculature e.g. duplex or computed tomographic angiography
- 6. WiFi score.
- 7. All concomitant medications.
- 8. Arterial duplex scan of the affected lower limb (standard of care for patients with severe limb threatening ischaemia).

Six months post discharge data collection (final follow-up):

The data collected here will relate to the time period between the procedure 6 months post discharge.

- 1. Weight/height, resting BP (anthropometric measurements).
- 2. Rutherford stage.
- 3. Ankle brachial pressure index.
- 4. Baseline full blood count results and routine biochemistry, including total cholesterol levels, and lipid profile.
- 5. Baseline serum creatinine and estimated glomerular filtration rate.
- 6. Chronic kidney disease status.
- 7. Diabetes status, duration of diabetes history, and current diabetes medication(s).
- 8. History of previous major cardiovascular events.
- 9. Results of cross-sectional imaging relating to the arterial vasculature e.g. duplex or computed tomographic angiography (all of these are routine care).
- 10. Smoking status.
- 11. Previous operations, including a full surgical and vascular history.
- 12. Results of cross-sectional imaging relating to the arterial vasculature e.g. duplex or computed tomographic angiography*
- 13. WiFi score.
- 14. Quality of life using the EuroQol-5D (EQ-5D) questionnaire.
- 15. Recording of all concomitant medications as reported by patients.

*Plaque analysis will be performed on the routine CT scans obtained at baseline. Additional plaque analysis will be undertaken on any additional CT angiograms which have been undertaken on any patient, for any reason during the six month follow-up period. We will use the scans in order to assess plaque volume (at any arterial segment treated with intravascular lithotripsy) and detailed plaque composition using a technique which our group pioneered and validated, described in detail before(23, 24). All PIs will be trained by the CI and [name] in this technique prior to commencing the study, using software which is already available at each clinical site (Aquarius TeraRecon). The scans will be analysed locally within seven days and we will report the following for each atherosclerotic plaque (i.e. target of intravascular lithotripsy treatment): volume of plaque which is calcified / fibro-calcific / fibrotic, lumen volume, plague volume, plague length. We will also report which vessels are patent and/or stenosed and/or occluded below the origin of the ipsilateral common iliac artery as well as the length (in mm) of each occluded segment. Inter- and intraoperator variability will be calculated and reported for the first five scans at each site (the CI and [name] will report the first five scans performed at each site together with the local PIs). Further, for each patient taking part we will report and record the Peripheral Arterial Calcium Scoring System (PACSS), a validated method to report degree of calcification, both before and after treatment(25).

The only study related data that is not collected as part of routine care is the completion of the EuroQol-5D (EQ-5D) questionnaire in relation to quality of life. The completion of a quality of life

CONFIDENTIAL Page 18 of 35 SHOCC Study IRAS: 299307

survey will be requested from all participating patients at baseline (pre-op) and at 6 months post discharge during their routine appointments.

Considerations due to COVID-19

We expect that COVID-19 will not have a major impact on inpatient and/or outpatient pathways for chronic limb threatening ischaemic and severe symptomatic PAD (our target population), given that these vascular pathologies are limb and/or life threatening. This has already been documented in our international study of vascular care during the COVID-19 pandemic (see: https://vascular-service-study/)

Patient involvement in this study falls alongside routine care and there is therefore no further risk of exposure to COVID-19 due to additional hospital visits as a result of taking part in this study.

Patients and staff will follow local trust COVID guidelines on the use of face masks and social distancing when they attend their routine hospital appointments.

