5. OBJECTIVES

Primary objective:

Investigate the effect of intravascular lithotripsy on the patency of a lower limb atherosclerotic lesion in patients with symptomatic PAD treated in the NHS, six months after the procedure.

Secondary objectives:

- 1. To investigate whether patients require further angioplasty or other procedures in the six months post intravascular lithotripsy.
- 2. To investigate whether patients suffer any of the following complications; stroke, transient ischaemic attack, myocardial infarction, or lower limb amputation in the six months post intravascular lithotripsy.
- 3. To investigate whether patients are readmitted to hospital for PAD related treatment in the six months post intravascular lithotripsy.
- 4. To investigate whether changes in atherosclerotic plaque consistency are observed within three days post intravascular lithotripsy
- 5. To gather information about how and why clinicians decided upon this choice of treatment over alternative methods available in the NHS.

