6.2 Primary and Secondary Endpoints/Outcome Measures

Primary outcome measure: patency of the treated arterial atherosclerotic lesion based on duplex ultrasound measurement at six months after the procedure has taken place (recorded as a binary outcome i.e. yes or no).

Secondary outcome measures:

During the inpatient stay:

Additional treatments during the index procedure, including other endovascular treatments (e.g. application of stent or drug coated balloon therapy or any other intervention deemed necessary by each operator)

All complications during the in-hospital stay:

Duration of in-hospital stay.

Thirty days after the procedure and at six months (final follow-up):

Re-intervention (open or endovascular - including re-intervention for other indications, which will be reported separately)

Lower limb amputation

Change in the treated atherosclerotic plaque consistency for patients requiring re-intervention or having additional imaging due to re-stenosis (secondary outcomes)

Patients' quality-of-life.

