8.7 Definition of End of Study

The end of study is the date of the last visit/ telephone follow up/ home visit of the last participant i.e. six months after the date the last patient has been recruited.

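### Outcomes are timed from the procedure but follow-up is collected from discharge, and the end-of-study definition adds a third anchor, recruitment

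*Protocol*

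**What the plan says.** **Procedure as anchor.** The primary objective (section 5) concerns patency "in patients with symptomatic PAD treated in the NHS, six months after the procedure". The primary outcome (section 6.2) is patency on "duplex ultrasound measurement at six months after the procedure has taken place". The later secondary outcomes, quality of life among them, stand in section 6.2 under "Thirty days after the procedure and at six months (final follow-up". Secondary objectives 1 to 3 in section 5 also count events over the six months following lithotripsy.

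**Discharge as anchor.** Section 8.3.1 titles its two follow-up lists "30 day post discharge data collection" and "Six months post discharge data collection (final follow-up". The period covered by the final list is described thus: "The data collected here will relate to the time period between the procedure 6 months post discharge" (a connecting word is evidently missing). The 30-day list has a matching sentence. The EQ-5D text later in section 8.3.1 also places the second questionnaire six months from discharge.

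**Recruitment as anchor.** Section 8.7 defines the end of study as the last participant's last visit, then restates it as "six months after the date the last patient has been recruited".

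Appendix A labels its columns only as 30 days and 6 months, so it does not settle the anchor. No visit window is given.

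**The concern.** The protocol fixes the time points twice, in different ways. A site working from section 6.2 would aim for a duplex six months after the procedure. A site working from section 8.3.1 would aim for six months after discharge. Followed as written, section 8.3.1 gives each patient an observation window that depends on that patient's stay. The 30-day and six-month proportions would then not be measured over a common time.

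This matters because section 4 says the study is to supply patency, amputation-free survival and re-intervention figures for planning a randomised trial, and it cites a trial reported only to 30 days. The short window is the more exposed, because a given stay is a larger share of 30 days than of six months. The six-month list also has no duplex item of its own, whereas the 30-day list has one. At six months the primary outcome rests on the general imaging-results items.

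**Working it through.** No power or sample-size formula applies; the check is date arithmetic.

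**The plan's own figure.** The Synopsis calendar reproduces: 3 + 9 + 6 + 3 = 21 months. Recruitment ends at month 3 + 9 = 12, and six months of follow-up end at month 18. (Section 11.2 speaks of one year for recording the 60 patients. That is a separate matter; the nine months of the Synopsis are used here.)

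**Inputs not in the documents.** Let L be the days from procedure to discharge and W the days from recruitment to procedure. Length of stay is collected, but no expected value is given. Consent is taken before the procedure (section 8.2; Appendix A puts it at the pre-operative baseline), but no interval is stated. I assume L = 0 to 30 days and W = 0 to 42 days. One month is 30.4375 days.

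**Formulas.**
- Close of the 30-day window, counted from the procedure: 30 + L days.
- Six-month visit minus the defined primary time point: L days.
- Last six-month visit minus the date in the section 8.7 restatement: W + L days.
- Calendar month of the last visit: 18 + (W + L)/30.4375.

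**Results.**

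| W (days) | L (days) | Six-month visit after the defined time point | Last visit after the section 8.7 restated date | Calendar month of last visit |
|---|---|---|---|---|
| 0 | 0 | 0 days | 0 days | 18.00 |
| 7 | 3 | 3 days | 10 days | 18.33 |
| 14 | 14 | 14 days | 28 days | 18.92 |
| 42 | 30 | 30 days | 72 days | 20.37 |

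Over L = 0 to 30, the 30-day window closes 30 to 60 days after the procedure, so it can double. The six-month window lengthens by at most 30/(6 × 30.4375) = 30/182.6, or about 16%.

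**An example.** A patient discharged on day 14 has an amputation on day 40. The 30-day collection runs to day 14 + 30 = 44, so it records the event. The thirty-day outcome of section 6.2 ends at day 30, so it does not.

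**Calendar.** The last visit would pass month 21 only if W + L exceeded 3 × 30.4375 = 91.3 days.

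**After re-anchoring to the procedure.** The six-month visit coincides with the primary time point. A gap of W days to the restated date in section 8.7 remains. It goes only if that restatement is deleted.

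**The case against.** The best defence is that little is lost. The final collection opens at the procedure and includes duplex results, so a routine scan done six months after the procedure falls inside it. Section 10.2 records adverse events with onset dates, so amputations and re-interventions that count as adverse events can be recounted from the procedure. The study is a single descriptive cohort, so no treatment contrast is biased. Visit windows are often left to an analysis plan or CRF guidance.

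Much of this stands. It rules out saying that the primary outcome is not collected at its defined time: the offset may be zero, and a correctly timed scan would be captured. It also means that the absence of a window is not, by itself, the fault. But onset dates do not re-time a scan or questionnaire taken at a discharge-anchored visit, and the protocol states two anchors rather than leaving one open.

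Four stronger inferences are tempting, and the text does not support them:
- *Final visits fall after the study ends.* The main clause of section 8.7 makes the last visit the end of study. Only the restatement puts the end earlier.
- *About 7 of 60 patients are affected.* This takes 60/9 = 6.7 recruits a month and assumes that every late recruit has a 30-day lag from recruitment to discharge. With no lag the count is zero.
- *Patients who lose the limb before discharge never enter the window.* The windows open at the procedure, and the day-of-discharge list records amputations and re-interventions up to discharge.
- *The sickest patients stay longest and so have the longest windows.* The documents give no data on length of stay by severity.

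**Conclusion.** The concern holds as an internal contradiction in the timing rules. Outcomes are defined from the procedure; the 30-day and six-month collections and the six-month EQ-5D are scheduled from discharge. Each window is lengthened by the patient's stay, and the schedule does not tie the primary duplex to its defined date. The size of the discrepancy is the length of stay, which the protocol does not give; the ranges shown rest on the assumed 0 to 30 days and shrink to nothing for same-day discharge.

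The section 8.7 fault is separate and smaller: the two halves of one sentence agree only if recruitment, procedure and discharge fall on the same day. It does not threaten the 21-month calendar for any lag considered here.

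This is a moderate and easily corrected inconsistency. It does not invalidate the study. It is best settled before data collection, because a scan done at the wrong time cannot be moved afterwards.

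**What to change.** - Use the procedure date as time zero in both follow-up lists of section 8.3.1, in the EQ-5D text of that section and in the column labels of Appendix A.
- State a visit window around the six-month duplex, so that it is clear which scan supplies the primary outcome.
- Count 30-day and six-month events from the procedure date. The in-hospital outcomes already form their own block in section 6.2 and can stay there.
- In section 8.7, delete the restatement that counts from recruitment, so that the end of study is the last participant's six-month post-procedure visit.

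The cost is a protocol wording change and revised CRF visit labels. With the assumed W of up to 42 days and all follow-up counted from the procedure, the last visit falls no later than month 18 + 42/30.4375 = 19.38, so the 21-month total can stay as it is.

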8.3.3 Optional Sub-study

A total of 20 consecutive patients will be invited to take part in sub-group analysis to document the impact of the intravascular lithotripsy on the calcified component of the atherosclerotic plaque. These patients will be recruited from the main site, University Hospitals of Leicester. We will stop recruiting in this sub-analysis once 20 patients have been recruited and have had their second CT scan three days after their intravascular lithotripsy procedure.

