11.2 The Number of Participants

We will record clinical characteristics for 60 patients treated with intravascular lithotripsy in the participating NHS centres over the period of one year. We will follow-up patients for six months. We expect a total of 60 patients to complete follow-up during this period of time, providing full clinical and imaging data, based on our national audits and UK PAD data for 2019-2021 based on the National Vascular Registry and the Vascular and Endovascular Research Network.

For the imaging sub-study (which is only taking part in Leicester i.e. the main study site), we have used a total of 182 patients' data (with femoro-popliteal disease) to estimate the sample size required, based on a study which is ongoing (using this type of plaque analysis for femoro-popliteal plaques). These 182 patients had their plaques analysed using the same technique that we are planning to use in this instance, prior to plain balloon angioplasty. Based on that data, we estimate a mean volume of 1.22mm3 for the calcified part of the femoro-popliteal plaque (based on Hounsfield units) and a standard deviation of 0.4 units; with the assumption we will document a reduction of the calcified component to 0.61 mm3 and to document this within a standard deviation of 0.4 units with a power of 90% and an alpha set at 0.05, we will require 20 patients to take part in this imaging sub-analysis.

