15. DATA HANDLING AND RECORD KEEPING

All study data will be entered on a REDCap based data collection form, created specifically for the study by the National Institute for Health Research Leicester Biomedical Research Centre Bioinformatics Hub staff. As per ICH GCP (Section 5.5), all electronic data entry systems are validated and Standard Operating Procedures are maintained by the National Institute for Health Research Leicester Leicester Biomedical Research Centre.

The participants will be identified by a study specific participant number and/or code in any database. The patient's name and any other identifying detail will NOT be included in any study data electronic file. No identifiable information will be shared between study sites at any point. Consent forms (signed) will be kept in study-specific site files at the NHS institutions taking part in this research in a locked safe NHS office as per standard Good Clinical Practice guidance and NHS policies.

Cross sectional imaging including duplex scans and computed tomographic angiograms will be analysed and reported locally at each NHS site by expert radiology doctors and the reports (fully anonymised) will be uploaded on the REDCap CRFs remotely. Further, the plaque analyses will be performed locally using computed tomographic angiograms as per the agreed study protocol and the relevant results will be reported (fully anonymised) on the CRFs for each patient. Non-anonymised scans will not be shared between sites at any point.

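### Protocol 8.3.1 and 15 make no provision for masked or random-order reading of the sub-study's paired CTs, and do not say that the reader-agreement scans are read independently or re-read

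*Protocol*

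**What the plan says.** **Where and when scans are read.** Protocol 8.3.1 states: "The scans will be analysed locally within seven days". The plaque-analysis note there covers baseline CTs and any further CT angiogram during the six-month follow-up, so it reaches the sub-study's second scan. Section 15 repeats that "the plaque analyses will be performed locally using computed tomographic angiograms".

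**Who reads.** Under 8.3.1 the site PIs are trained in the technique by the chief investigator and one other person. Section 8.1 describes the investigators who approach patients as their usual clinicians.

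**Agreement check.** Section 8.3.1 plans inter- and intra-operator variability on the first five scans at each site. The chief investigator and a second reader "will report the first five scans performed at each site together with the local PIs". No independent read, locked result or repeat read is described.

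**The comparison.** Section 8.3.3 recruits 20 patients at the main site and stops once they "have had their second CT scan three days after their intravascular lithotripsy procedure". Section 11.2 sizes it: "we estimate a mean volume of 1.22mm3 for the calcified part of the femoro-popliteal plaque", with "a standard deviation of 0.4 units", and "with the assumption we will document a reduction of the calcified component to 0.61 mm3". It concludes that "with a power of 90% and an alpha set at 0.05, we will require 20 patients to take part in this imaging sub-analysis". This is the only power calculation in the protocol.

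**Masking.** The protocol mentions no masking of image readers. Its one reference to blinding is the data-analysis report sent to the funder (Section 18).

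**The concern.** The sub-study result is a within-patient change with no control arm. Any systematic tendency to read less calcium on the post-procedure scan adds directly to the estimated effect, and no later analysis can separate the two. The conditions for such a tendency are present. One site's team reads both scans of each pair, the expected direction and size are written into Section 11.2, and nothing hides which scan is which.

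The agreement check has a separate weakness. If the five scans per site are reported by consensus, inter-operator variability is not estimated at all. Intra-operator variability needs a second read by the same person, and none is described.

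Section 4 presents the mechanistic result as essential before any randomised study, so a false or exaggerated fall in calcified volume would carry forward into later planning.

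**Working it through.** **1. Inputs.** From Section 11.2: baseline mean 1.22 mm³, assumed post-procedure mean 0.61 mm³, SD 0.4, power 90%, alpha 0.05, N = 20. Assumed here because the protocol does not say: a two-sided test, a paired t-test for the before/after comparison, and the size of any reader shift.

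**2. The plan's own figure.** The difference is 1.22 − 0.61 = 0.61, which is 50% of baseline. The two-independent-group formula gives n per group = 2 × (1.960 + 1.282)² × 0.4² / 0.61² = 9.04, rounded up to 10, so 20 in total. The stated 20 is reproduced.

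**3. SD of the within-patient change.** The protocol does not say whether 0.4 describes single volumes or changes. If it describes single volumes, SD of change = 0.4 × √(2(1 − ρ)), where ρ is the within-patient correlation:
- ρ = 0: 0.566
- ρ = 0.5: 0.400
- ρ = 0.75: 0.283

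**4. Sensitivity of 20 pairs.** For the assumed fall of 0.61, power with 20 pairs is 99.5% at SD 0.566 and above 99.9% at SD 0.4. A test this sensitive to a true change also responds to a small artefact.

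**5. Effect of a reader shift when nothing has changed.** The true change is set to 0 and post-procedure readings are shifted by b. The test statistic then follows a non-central t distribution with 19 degrees of freedom and non-centrality b / (SD/√20); the critical value is 2.093. For b = 10% of baseline = 0.122 and SD 0.4, the SE is 0.4/√20 = 0.089 and the non-centrality is 1.36.

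Probability of p<0.05, nominally 5%:

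| Shift, % of baseline (mm³) | SD 0.283 | SD 0.4 | SD 0.566 |
|---|---|---|---|
| 5% (0.061) | 15% | 10% | 7% |
| 10% (0.122) | 45% | 25% | 15% |
| 15% (0.183) | 78% | 49% | 28% |

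**6. Scale against the planned effect.** A 10% shift is 0.122 of the assumed 0.61, or one fifth of it; a 15% shift is three tenths. Neither alone would look like the planned halving. The risk is a significant result with no true change, or an exaggerated estimate when a true change exists.

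**The case against.** **The protocol does not say that scans are read unblinded or in time order.** A reader might infer both from the seven-day rule and the lack of masking text. The inference is plausible but goes too far. Section 8.3.1 does not say when the seven days start, so both scans of a pair could be read in one sitting, and an imaging manual or SAP that is not shown could add masking. What stands is narrower: the protocol fixes where and how fast scans are read and makes no provision for masking or order. If the seven days run from each scan, a batched read after the last sub-study scan would depart from that rule, and a later analysis plan could not mask reads already made.

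**Reporting together may mean reporting in addition to the local PI.** The phrase explains how inter-operator variability is obtained, which needs more than one read, so separate reads may well be intended. It is therefore not established that the agreement figures are inflated; independence and repetition are simply not stated.

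**Joint reads do not hide the before/after bias.** It is tempting to link the two parts this way. Independent readers who share the same expectation would also agree with each other, and the first five scans need not include any post-procedure scan. The two weaknesses are separate.

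**The measure is partly objective.** The study title refers to automated plaque analysis, and Section 11.2 bases calcified volume on Hounsfield units. This may make any shift small. It does not show that the shift is nil, since the protocol itself plans an operator-variability check.

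**The scope is limited.** This concerns secondary objective 4 at one site. The primary outcome, duplex patency, is untouched.

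**Conclusion.** The point holds as an omission in the reading procedure. The protocol prescribes local reading within seven days with no provision for masking or random order, so its only powered comparison, uncontrolled and in 20 patients, is exposed to systematic reader bias. Under an assumed 10% shift with no true change, p<0.05 would occur in about 15% to 45% of studies (SD of change 0.57 to 0.28), against 5%. The shift is an assumption, since the documents give none, and the range also rests on a two-sided paired t-test. A shift of that size could not alone generate the assumed 50% fall.

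The agreement check is under-specified, because independent and repeated reads are not stated. The documents do not show that bias is present, that readers are knowingly unmasked, or that the agreement reads are joint. The change is worth making because it is inexpensive and has to be in place before the scans are read.

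**What to change.** **(a) Sections 8.3.1 and 8.3.3, sub-study comparison.** Base it on a masked read of the paired scans (20 patients × 2 = about 40) by the existing readers, in random order, after the last sub-study scan. Remove dates and labels, and crop both scans of a pair to the same treated segment. Cropping is needed because Section 14.7 describes the second CT as a limited scan, usually about 30 cm long, so its field of view could identify it. Sub-study patients also belong to the main cohort, so either exempt their scans from the seven-day read or state that the masked read is a re-read and alone feeds the comparison.

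**(b) Section 8.3.1, agreement scans.** State that the local PI and the central readers read the five scans separately and lock their results before discussion, and that a repeat read is made for intra-operator variability. This makes the agreement figures valid; it does not itself guard against before/after bias.

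**Cost.** Protocol wording, local anonymisation and cropping, with no extra scan, radiation or reader. Sub-study results wait for the last scan, up to about 20 baseline scans may be read twice, and some agreement scans are re-read. A visible stent may still reveal the time point, so masking will be incomplete in some patients. N stays at 20.
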